2.7 Anti-drug Antibody Analysis (ADA)

Treatment-emergent ADA consists of treatment-induced ADA and treatment-boosted ADA, as defined below:

- Treatment-induced ADA: Confirmed positive ADA developed de novo after drug administration in patients without preexisting (baseline) confirmed positive ADA
- Treatment-boosted ADA: Confirmed positive ADA after drug administration with ADA titer > 4x baseline ADA titer in patients with preexisting (baseline) confirmed positive ADA

ADA status consists of ADA positive and ADA negative, as defined below:

- ADA positive is defined as patients with confirmed ADA positive results at any visit.
- ADA negative is defined as patients with ADA negative results at all visits, including patients with non-confirmed ADA positive results at screening

ADA post-dose is defined below:

- ADA positive is defined as patients with confirmed ADA positive results at any visit after baseline visit.
- ADA negative is defined as patients with ADA negative results at all visits after baseline visit.

2.8 Analysis Visit

2.8.1 Analysis item except PK data, 24-hour Holter ECG Extraction

Assessment	Analysis item	Analysis visit
Efficacy	24-hour ABPM (SBP and DBP)	Baseline, Month 3, Month 6
	OBP (SBP and DBP)	Baseline, Day 2, Day 3, Day 8, Day 15, Month 1, Month 2, Month 3, Month 4, Month 5, Month 6, Month 9 and Month 12
	HBPM (SBP and DBP)	Baseline, Week X (at least once per week after Day 2)
Pharmacodynamic (PD)	Serum AGT	Baseline, Day 8, Day 15, Month 1, Month 2, Month 3, Month 6, Month 9 and Month 12
Biomarker	RAS (Renin concentration, Renin activity assessment and Aldosterone assessment)	Baseline, Month 1, Month 2, Month 3 and Month 6
Safety	Vital sign	Baseline, Day 2, Day 3, Day 8, Day 15, Month 1, Month 2, Month 3, Month 4, Month 5, Month 6, Month 9 and Month 12
	Weight, Height and BMI	Baseline and Month 6
	Single 12-lead ECG	Baseline and Month 6
	Hematology	Baseline and Month 6
	Serum Chemistry	Baseline, Day 8, Day 15, Month 1, Month 2, Month 3, Month 4, Month 5, Month 6, Month 9 and Month 12
	Liver Function Tests	Baseline, Day 8, Day 15, Month 1, Month 2, Month 3, Month 4, Month 5, Month 6, Month 9 and Month 12
	Urinalysis	Baseline and Month 6
	Coagulation	Baseline and Month 6
	Glycemic Assessment	Baseline
	Pregnancy Testing/FSH	Baseline
Optional research samples (urine, plasma, serum)	-	Baseline, Month 3 and Month 6
ADA	ADA and titer results	Baseline, Month 1, Month 3, Month 6

Abbreviations: ABPM=ambulatory blood pressure monitoring; ADA=anti-drug antibody;

AE=adverse event; AGT=angiotensinogen; DBP=diastolic blood pressure;

ECG=electrocardiogram; PD=pharmacodynamics; PK=pharmacokinetics; RAS = renin-angiotensin system; SBP=systolic blood pressure; DNA=deoxyribonucleic acid; FSH=follicle stimulating hormone;

2.8.2 PK 24-hour and Holter ECG Extraction

Analysis item	Analysis visit	Analysis timepoint
Blood PK Sample	Baseline	Predose
	Day 1	30 minutes postdose 1 hour postdose 2 hours postdose 3 hours postdose 4 hours postdose 6 hours postdose 8 hours postdose 12 hours postdose 16 hours postdose
	Day 2	24 hours postdose
	Day 3	48 hours postdose
Pooled urine for PK	Baseline	Predose
	Day 1	>0-6 hours postdose >6-12 hours postdose >12-24 hours postdose
24-hour Holter ECG Extraction	Baseline	Predose
	Day 1	30 minutes postdose 1 hour postdose 2 hours postdose 3 hours postdose 4 hours postdose 6 hours postdose 8 hours postdose 12 hours postdose 16 hours postdose
	Day 2	24 hours postdose

2.8.3 Analysis Visit for Escape Antihypertensive Medication

Escape antihypertensive medication is defined as any antihypertensive medication that was started after the first dose.

The analysis visit for Escape Antihypertensive Medication will be the visits that were censored. The Office BP records that were censored will be used to identify the visits for Escape Antihypertensive Medication.

3. Case and Data Handling

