2.2 Analysis Population

Analysis Sets	Definitions
Safety Analysis Set	All patients who received any amount of study drug. All by-treatment analyses based on the Safety Analysis Set will be grouped according to the treatment actually received.
PK Analysis Set	All patients who received 1 full dose of zilebesiran and have at least 1 evaluable postdose PK assessment.
PD Analysis Set	All patients who received 1 full dose of study drug. All by-treatment analyses based on the PD Analysis Set will be grouped according to the treatment actually received.
Full Analysis Set	All randomized participants who received any amount of study drug. All by-treatment analyses based on the Full Analysis Set will be grouped according to the randomized treatment arm.

Safety will be analyzed using the Safety Analysis Set. The PK and PD Analysis Sets will be used to conduct PK and PD analyses, respectively. Efficacy will be analyzed using the Full Analysis Set.

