2.6 Efficacy Assessment

2.6.1 SBP and DBP

Analysis using censoring and analysis using all collected data will be conducted for ABPM and Office Blood Pressure. Analysis using all collected data will be conducted for HBPM

- Censoring data: ABPM/Office Blood Pressure that assessed while patients are on and within 2 weeks after stopping any escape anti-hypertensive medication will be excluded for analysis.
- All collected data: all collected BP data is included in analysis, regardless of the anti-hypertensive escape medication.

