7.1.10 Proportion of Patients with Escape Antihypertensive Medication by Visit

Target population	:	Full Analysis Set
Analysis Items	:	Patients with Escape Antihypertensive Medication
Group	:	Placebo, Zilebesiran 300 mg, Zilebesiran 600 mg, Total zilebesiran, Overall Total
Time of analysis	:	Refer to section 2.8.3
Content of analysis	:	
 • The number of patients with Escape Antihypertensive Medication and the percentage will be calculated for each group.
Definition	:	
 • The denominator of proportions is the target population by groups.

8. Pharmacodynamic Evaluation

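### The escape-medication table counts use only where a scheduled office BP reading was censored and divides by the whole Full Analysis Set, so it misstates use by visit and gives no count of escape by Month 6

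*SAP*

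**What the plan says.** SAP 2.8.3 gives the definition: "Escape antihypertensive medication is defined as any antihypertensive medication that was started after the first dose". It then ties the table to BP censoring: "The analysis visit for Escape Antihypertensive Medication will be the visits that were censored", and "The Office BP records that were censored will be used to identify the visits for Escape Antihypertensive Medication".

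The censoring rule is in SAP 2.6.1: "ABPM/Office Blood Pressure that assessed while patients are on and within 2 weeks after stopping any escape anti-hypertensive medication will be excluded for analysis".

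SAP 7.1.10 is a by-visit table: "The number of patients with Escape Antihypertensive Medication and the percentage will be calculated for each group". For the percentage, "The denominator of proportions is the target population by groups". The target population there is the Full Analysis Set (FAS), defined in SAP 2.2 as "All randomized participants who received any amount of study drug", so it has the same size at every visit.

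Three other rules bear on this. SAP 3.4 imputes no missing data. SAP 3.5.2 leaves post-baseline unscheduled visits out of by-visit analyses. SAP 2.8.1 lists the office BP visits from the time treatment is generally permitted as "Month 3, Month 4, Month 5, Month 6, Month 9 and Month 12".

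**The concern.** Whether a patient is on escape medication is a fact about medication dates. Under 2.8.3 it enters the table only if there is a scheduled office BP reading to carry it and that reading was censored. A patient without a reading is then indistinguishable from a patient who needed no escape. The 2-week tail has a purpose in BP censoring, where it allows for carry-over. Reused here, it turns patients who have stopped into users.

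Escape treatment is permitted to treat to target from Month 3 (Protocol 5.7.2, Table 3), and Month 6 BP is a secondary endpoint. The SAP presents Month 6 BP both with and without readings taken under escape. To understand why the two versions differ between arms, a reader needs a reliable count of escape use by arm, and 7.1.10 is the table that should supply it.

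**Working it through.** The documents give no figure for escape use, so there is none to reproduce. The check applies the stated rules to the stated schedule.

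**Inputs.** Nominal office BP days from Month 1 are 29, 57, 85, 113, 141, 169, 253 and 337 (Protocol Table 1). The gaps are 28 days through Month 6, then 84 and 84. Visit windows are ±5 days at Months 1 and 2, ±7 at Months 3 to 6, and ±14 at Months 9 and 12. The tail is 14 days (SAP 2.6.1). The planned arm size is 12.

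**1. No reading at the visit.** A patient with no scheduled office BP adds 0 to the numerator and 1 to the denominator.
- Each escape user who leaves lowers the arm's percentage by 1/12 = 8.3 points at every later visit.
- Illustration (invented counts): 4 of 12 start escape and 2 of these 4 withdraw. The later table shows 2/12 = 16.7%. Among those still observed it is 2/10 = 20.0%. The share that ever started is 4/12 = 33.3%.
- Second illustration (invented counts): 2 non-users leave and 6 of the remaining 10 are on escape. The table shows 6/12 = 50% against 6/10 = 60%.
- A missed office BP has the same effect at that visit. So does an early-termination reading that falls between the SAP 3.5.2 windows, for example on Days 93 to 105, because it maps to no analysis visit.

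**2. Tail.** A reading 1 to 14 days after the last day on drug is censored, so that patient is counted as a user at that visit.

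**3. Courses between visits.** Take visits on days a and b. A course is missed if it starts on day a + 1 or later and its last day is b − 15 or earlier. The longest missed course is therefore (b − a) − 15 days.
- 28-day gap: 28 − 15 = 13 days.
- 84-day gap: 84 − 15 = 69 days.
- At the window extremes: 28 + 7 + 7 − 15 = 27 days between Months 3 and 6; 84 + 7 + 14 − 15 = 90 days for Months 6 to 9; 84 + 14 + 14 − 15 = 97 days for Months 9 to 12.

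If start days are uniform within a gap (an assumption), the share of courses of L days that is missed is (gap − 14 − L)/gap, or zero if negative:

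| Course length (days) | 28-day gap | 84-day gap |
|---|---|---|
| 7 | 7/28 = 25% | 63/84 = 75% |
| 14 | 0 | 56/84 = 67% |
| 28 | 0 | 42/84 = 50% |
| 42 | 0 | 28/84 = 33% |
| 56 | 0 | 14/84 = 17% |
| 70 | 0 | 0 |

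Under the same assumption, 14/28 = 50% of 7-day and 14-day courses in a 28-day gap are counted only at a visit after the drug was stopped. In an 84-day gap it is 14/84 = 17% of courses of 7 to 70 days.

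**4. Other outputs.** SAP 12.5.1 gives patients with concomitant antihypertensives by arm, and listing 13.9 shows the individual records. SAP 12.5.1 sets no period and no Month 6 cut. The primary analysis runs when the last patient reaches Month 6 or withdraws (SAP 2.4), so patients enrolled earlier may already contribute follow-up data. The concomitant definition in SAP 2.5.3 also includes drugs begun before dosing and continued, which the escape definition does not.

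**The case against.** Several objections have force.

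- A reader might infer that the table ignores medication dates. It does not: the censoring flag can only be set from escape start and stop dates. What is lost is use that has no scheduled office reading to carry it.
- A reader might infer that ever-use is reported nowhere. Because earlier antihypertensives are washed out before randomization, SAP 12.5.1 comes close to ever-use by arm over the data available. It lacks the Month 6 cut and the escape definition.
- Before Month 6 the loss of courses is small: on nominal days nothing of 14 days or longer disappears. Escape in that period is for persistent elevation, which makes very short courses unlikely, although the documents give no durations. The 69-day figure belongs to follow-up and says nothing about Month 6.
- Counting the tail makes the table agree with the office BP exclusions in SAP 7.1.2 and 7.1.9. That is a real use, but it is a count of censored readings, not of patients on drug.
- The FAS denominator follows the SAP-wide convention in 4.1.3. Counts are printed beside percentages, and withdrawals are tabulated in 5.2. A reader can rescale in part, but cannot tell from these tables who missed an office BP or whether those who left were escape users.
- Withdrawal may be low. This is a single-dose study and patients are encouraged to stay.

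Escape use is not a listed endpoint, and all analyses are descriptive.

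**Conclusion.** The concern holds for table 7.1.10. As defined, the table understates escape use when patients leave or miss office BP (8.3 points per escape user lost in an arm of 12), counts patients as users for up to 14 days after stopping, and misses short courses before Month 6 and considerably longer ones afterwards. The denominator and the absence of a count by Month 6 matter most. For sustained therapy before Month 6 the timing errors are minor.

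A reader might go further and conclude that the Month 6 BP results are themselves distorted. The documents do not support that: the all-collected and censored summaries in SAP 7.1.1 and 7.1.2 are produced independently of this table. What suffers is the description of escape use by arm that accompanies them.

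The day limits rest on nominal visit days unless window extremes are stated, and on reading the tail as days 1 to 14 after the last day on drug. The shares of missed courses assume uniform start days, and the dropout illustrations use invented counts.

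**What to change.** Rewrite SAP 2.8.3 and 7.1.10 so that the table is derived directly from escape start and stop dates, using the date-imputation rules already in SAP 3.1.2.

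- At each visit, report by arm the number on escape on the visit date, with patients still in the study as denominator. Alternatively, keep the FAS and add a row for patients not in the study or with missing status.
- Add the cumulative number and proportion of FAS patients who started escape by Months 3 and 6, and by Months 9 and 12 at the final analysis. A Kaplan-Meier display of time to first escape is optional with 12 patients per arm.
- Keep the 2-week tail for BP censoring only. If agreement with 7.1.2 and 7.1.9 is wanted, show the number of censored office BP records as a separate row.

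The cost is SAP wording and one re-programmed table. Medication changes are already recorded on the eCRF (Protocol 5.8), so no new data are needed and patient management is unchanged.

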3.1 Handling of missing or partial dates

3.1.1 Handling of missing and partial dates for adverse events

a) Tables

For records with fully or partially missing AE onset date, conventions for the imputation is as below:

- AE onset dates with missing day and non-missing month will be imputed to occur on the first day of the non-missing month, except for AEs occurring in the first month of

dosing, in which case the date will be the first day of dosing.

- AE onset dates with missing month will be imputed to occur on the first day of the non-missing year (i.e., January 1), except for AEs occurring in the first year of dosing, in which case the date will be the first day of dosing.
- If year of the AE start date is missing, the onset date will be imputed as the first day of dosing, except if it can be unequivocally determined (from the partial or complete stop date) that the event occurred prior to the first dose of study drug, in which case the AE onset date will not be imputed.
- If an imputed onset date is after the collected AE end date, the end date will be used as the imputed onset date.

b) Listings:

Imputed dates will not be presented in the listings.

3.1.2 Handling of missing and partial dates for concomitant medication

a) Tables

For medications with partial start or end dates: the first day/month will be imputed for start date, and the last day/month will be imputed for end date.

For medications with a completely missing start date, the medications will be considered as started one day prior to the first dose of study drug. If an imputed start date is after the collected end date, the end date will be used as the imputed start date.

For medications with a completely missing end date or an imputed end date that is after the earliest date of: end of study date, data cutoff date or date of death, the latter (i.e., the earliest date of: end of study date, data cutoff date or date of death) will be used as the imputed end date.

b) Listings:

Imputed dates will not be presented in the listings.

3.1.3 Handling of missing and partial dates except concomitant medication and adverse events

Imputation for missing dates is not considered.

3.2 Handling of PK data and Urine PK data

3.2.1 Handling of BLQ values

3.2.1.1 For Non Compartmental Analysis (NCA)

BLQ value is imputed to 0 before Tmax and left as missing after Tmax.

3.2.1.2 For figures and summary tables of concentration

BLQ is imputed to 0

For semi-logarithmic Scale figures, BLQ value is imputed to 0.01, instead of zero.

3.2.1.3 For listings of concentration

BLQ values are reported as the raw data.

3.2.2 Handling of PK parameter

The PK parameters $t_{1/2}$, AUC_{0-inf} , CL/F , and V_z/F will be presented for only subjects in whom λ_z can be estimated. AUC_{0-inf} will be reported for only subjects in whom $AUC_{\%extrap} \leq 25\%$.

3.3 Handling of Safety Data

3.3.1 Handling of Adverse Events

Adverse events will be coded according to the Medical Dictionary for Regulatory Activities and summarized by System Organ Class (SOC) and PT by dose level and overall. AEs, SAEs, study-drug related AEs, AEs leading to withdrawal from study, and AEs leading to death will be summarized by SOC and PT for each treatment arm and overall. Additionally Hepatic AEs, including AEs of LFT abnormalities, Hyperkalemia, Hypotension, Potential Hypotension and Acute renal failure will be summarized by SOC and PT for each treatment arm and overall. AEs, SAEs, and study-drug related AEs will be summarized by PT for each treatment arm and overall. By-patient listings will also be provided.

1) For summary tables

Treatment-emergent Adverse Event from throughout the double-blind treatment period will be included.

- First study drug administration date Onset date of Adverse Events \leq first study drug administration + 169 days.
- Treatment related AEs that occur after 169 days of first study drug administration are also counted as TEAE.

AEs with Missing or partial dates will be handled per section 3.1.1.

An AE with missing severity will be assumed to be severe.

An AE with missing study drug relatedness will be assumed to be related.

2) For listings

All Adverse Events from screening period through safety-follow up period will be included.

Missing study drug relatedness and missing severity will be presented as collected in the EDC.

3.3.1.1 Number of Patients with Events

If more than one Adverse Event occurred in a same patient (Relationship of the Adverse Event to Study drug if counting the Relationship of the Adverse Event to Study drug, Serious Adverse

Events if counting the Serious Adverse Event, Adverse Event of Clinical Interest if counting Adverse Event of Clinical Interest, Adverse Event Severity if counting Adverse Event Severity), the number of patients with event occurrence will be counted as one (summary processing performed).

A patient with more than one occurrence of the same AE in a particular SOC/PT will be counted only once for the SOC/PT using the severest event (summary processing performed).

3.3.1.2 Number of Events

If more than one Adverse Event occurred in a same patient (Relationship of the Adverse Event to Study drug if counting the Relationship of the Adverse Event to Study drug, Serious Adverse Event if counting the Serious Adverse Event, Adverse Event of Clinical Interest if counting Adverse Event of Clinical Interest, Adverse Event Severity if counting Adverse Event Severity), each event will be counted respectively (no summary processing performed).

3.3.2 Handling of Prior and Concomitant Medication, Prior and Concomitant Anti-hypertensive Medication

In the tabulation of prior/concomitant medications (System organ class, High level term, Preferred Term), if the same patient uses multiple medications corresponding to the same System organ class, High level term, Preferred Term code when counting the Preferred Term, High level term when counting High level term, System organ class when counting System organ class, the data will be tabulated as one drug.

3.3.3 Handling of all evaluation safety items except for Adverse Events, Prior and Concomitant Medication, Prior and Concomitant Anti-hypertensive medication

- Missing data will not be imputed.
- If outliers are excluded from the analysis, they will be specified, and the reasons for exclusion should be stated.
- For the listing and figure by patient, not only scheduled visit data but also unscheduled visit data will be used. For figures by patient based on Labs, only central labs will be presented.
- For the table and figure of summary statistics, only scheduled visit data will be used. For tables and figures of summary statistics based on Labs, only central labs will be presented.

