5.7. Monitoring for Potential Clinical Events

5.7.1. Monitoring and Approach for Potential Hypotension

Hypotension is an obligate risk of antihypertensive medications. In addition to office blood pressure monitoring, outpatient blood pressure will be monitored weekly with HBPM to ensure the early detection of potential hypotension. Whenever possible, management decisions will be based on blood pressure measurements confirmed by office blood pressure.

The following management recommendations for hypotension are provided:

- Patients who experience low blood pressure that is associated with symptoms should promptly seek medical evaluation at the clinical study site or another hospital setting. Clinical study site evaluation for low blood pressure should include the assessment of orthostatic blood pressure (seated to standing).
- The Investigator should consider downtitration or interruption of oral antihypertensives (if taking) if confirmed office SBP <90 mmHg or if clinical symptoms, such as lightheadedness or dizziness, develop coupled with a significantly lower SBP compared to prior visits (ie, SBP <100 mmHg).
- Clinically significant events discovered during the course of a patient's general medical care should be promptly communicated to the site and evaluated by the Investigator, especially if hypotension is noted. Patients will carry Institutional Review Board (IRB)/Independent Ethics Committee (IEC)-approved patient cards to facilitate this physician-to-physician communication.
- If hypotension is confirmed, serum electrolytes and creatinine should be measured and any oral antihypertensive(s) should be downtitrated or interrupted per Investigator judgement as outlined above.
- The frequency of blood pressure and laboratory monitoring (serum electrolytes and creatinine) should be increased during intercurrent illnesses that predispose patients to dehydration (eg, vomiting or diarrhea that persists for more than 24 hours) or when symptoms consistent with decreased effective circulating volume (eg, presyncopal symptoms, unexplained falls, decreased urine output) manifest, even if a patient's recent blood pressure measurements have been normal.

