5.8.1. Oral Antihypertensive Medication

Individual initiation and modification of oral antihypertensive medications per Investigator judgement are permitted throughout the study if required to treat clinically significant blood pressure elevation (Section 5.7.2). In addition, after Month 3, oral antihypertensive medications may also be added per Investigator judgement for persistent elevations in blood pressure above recommended target per treatment guidelines.[Umemura 2019; Williams 2018] All oral antihypertensive medication that are dosed once daily should be taken in the morning.

Serum electrolytes and creatinine should be measured at a central or local laboratory approximately 2 weeks after any antihypertensive addition or dose titration.

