6.5.5. Clinical Laboratory Assessments

Clinical laboratory assessments are listed in [Table 6](#) and will be assessed as specified in the Schedule of Assessments ([Table 1](#)).

Clinical laboratory tests will be evaluated by a central laboratory. Specific instructions for transaminase elevations are provided in Section 5.7.5. For any other unexplained clinically relevant abnormal laboratory test occurring after study drug administration, the test should be repeated and followed up at the discretion of the Investigator until it has returned to the normal range or stabilized, and/or a diagnosis is made to adequately explain the abnormality. Additional safety laboratories and assessments as indicated by the clinical situation may be requested. While local laboratory results may be used for urgent clinical decisions, on the day of the assessments, all laboratory assessments specified in [Table 6](#) that are performed at the clinic should also be sent in parallel to the central laboratory.

Blood samples collected for RAS biomarkers should be collected in the morning and in the seated/upright position (after blood pressure measurements and before any assessments collected in the supine position). Blood samples for laboratory evaluation should be collected after the completion of blood pressure assessments.

Spot urine collections for albumin and creatinine should be obtained in the morning.

For any safety event or laboratory abnormality, additional laboratory assessments, imaging, and consultation may be performed for clinical evaluation and/or in consultation with the Medical Monitor; results may be collected and should be included in the clinical database.

Table 6: Clinical Laboratory Assessments

Hematology	
Complete blood count with differential	
Serum Chemistry	
Sodium	Potassium
BUN	Phosphate
Uric acid	Albumin
Total protein	Calcium
Glucose	Bicarbonate
Creatinine and eGFR ^a	Chloride
Triglycerides	
Liver Function Tests	
AST	ALP
ALT	Bilirubin (total and direct)
GGT	
Urinalysis	
Visual inspection for appearance and color	Bilirubin
pH (dipstick)	Nitrite
Specific gravity	RBCs
Ketones	Urobilinogen
Albumin	Leukocytes
Glucose	Microscopy (if clinically indicated)
Protein	
Coagulation	
Prothrombin time	International Normalized Ratio
Partial Thromboplastin Time	
Glycemic Assessment (see Section 6.5.5.1)	
HbA1c	
Immunogenicity (see Section 6.5.5.2)	
Anti-drug antibodies	
Pregnancy Testing/FSH Screening (see Section 6.5.5.3)	

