3.5.2 Time Windows

For tables and figures, the visit will be defined as the following:

- For actual visits on EDC except unscheduled visit, end of treatment visit, early termination visit and end of study visit, the visit will be used as it is for analysis.
- For actual visits on EDC of unscheduled visits, the data from this visit will be used to calculate baseline, worst post baseline, and maximum post baseline only. Post baseline unscheduled visits will not be considered for by-visit analysis.
- For actual visits on EDC of end of treatment visit, early termination visit and end of study visit, the analysis visit will be as the following table. The day of administration of the investigational drug is defined as “Day 1”

Analysis visit	Reference date	Time window
Day 8	Day 8	Day 5 ~ Day 11
Day 15	Day 15	Day 12 ~ Day 18
Month 1	Day 29	Day 24 ~ Day 34
Month 2	Day 57	Day 52 ~ Day 62
Month 3	Day 85	Day 78 ~ Day 92
Month 4	Day 113	Day 106 ~ Day 120
Month 5	Day 141	Day 134 ~ Day 148
Month 6	Day 169	Day 162 ~ Day 176
Month 9	Day 253	Day 239 ~ Day 267
Month 12	Day 337	Day 323 ~ Day 351

For all listings, the visit will be displayed as the visit on EDC.

4. Statistical Analysis

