Definitions	:	
 • The denominator of proportions is the target population by groups.

12.4.3 Summary of Post-Baseline Potentially Clinically Significant Abnormalities for Clinical Laboratory Data during 6-Month DB Period

Target population	:	Safety Analysis Set
Analysis Items	:	Hematology, Serum Chemistry
Group	:	Placebo, Zilebesiran 300 mg, Zilebesiran 600 mg, Total zilebesiran, Overall Total
Time of analysis	:	Refer to section 2.8.1
Content of analysis	:	
 • Calculate the number of patients and the percentages by groups, analysis items and categories • Category for Hematology is as follows Hemoglobin (g/L): <100 Lymphocytes ($\times 10^9/L$): <0.8, <0.5, >12 Neutrophils ($\times 10^9/L$): <1.5, <1.0, ≥ 12 Platelet Count ($\times 10^9/L$): <75, <50, ≥ 600 WBC Count ($\times 10^9/L$): <3.0, ≥ 16 • Category for Serum Chemistry is as follows: Albumin (g/L): <30 Calcium (mmol/L): <2.0, >2.9 Creatinine (umol/L): >2xBaseline, >3xBaseline or >4 mg/dL eGFR(mL/min/1.73m²): $\geq 30\%$ Decrease from Baseline Plasma Glucose (mmol/L): <3.0, ≥ 13.9 Serum Glucose (mmol/L): <3.0, ≥ 13.9 Phosphate (mmol/L): <0.6 Potassium (mmol/L): <3.0, >5.5, >6.0 Sodium (mmol/L): <130, >155 • Calculate for Serum Chemistry with Confirmed by repeat measure is as follows: Creatinine (umol/L): >2xBaseline, Confirmed by repeat measure eGFR(mL/min/1.73m²): $\geq 30\%$ Decrease from Baseline, Confirmed by repeat measure Potassium (mmol/L): >5.5, Confirmed by repeat measure
Definitions	:	
 • The denominator of proportions is the target population by groups. • Repeat measure: the abnormal criteria was present for consecutive (non-missing) collections.

12.4.4 Shifts from Baseline to Worst Post-Baseline in eGFR (mL/min/1.73m²) during 6-month DB Period

Target population	:	Safety Analysis Set
Analysis Items	:	eGFR (mL/min/1.73m ²)
Content of analysis	:	
 • Create shift table for baseline to Worst post-baseline data by category. • Category is as follows: >=90 (mL/min/1.73m²), 60 to <90 (mL/min/1.73m²), 45 to <60 (mL/min/1.73m²), 30 to <45 (mL/min/1.73m²), 15 to <30 (mL/min/1.73m²), <15 (mL/min/1.73m²), Missing, Total
Definition	:	• The denominator of proportions is the target population by groups.

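### Potassium and creatinine results obtained only at a local laboratory are left out of the by-arm laboratory tables and reach by-arm counts only if reported as adverse events

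*SAP*

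**What the plan says.** SAP 3.3.3 covers safety data other than adverse events and medications. It states "For tables and figures of summary statistics based on Labs, only central labs will be presented", directly after "For the table and figure of summary statistics, only scheduled visit data will be used". For patient-level plots it adds "For figures by patient based on Labs, only central labs will be presented". Listings use scheduled and unscheduled data and carry no central-only limit. They include the listings of patients with potassium above 5.5 mmol/L (13.40) and with a 30% eGFR reduction (13.41).

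SAP 3.5.2 says of unscheduled visits that "the data from this visit will be used to calculate baseline, worst post baseline, and maximum post baseline only".

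SAP 12.4.3 counts patients by arm who cross laboratory thresholds in the double-blind period, among them "Potassium (mmol/L): <3.0, >5.5, >6.0", multiples of baseline creatinine, and an eGFR fall of at least 30%. SAP 12.4.4 tabulates the shift to the worst eGFR category.

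Protocol 5.8.1 says "Serum electrolytes and creatinine should be measured at a central or local laboratory approximately 2 weeks after any antihypertensive addition or dose titration". Protocol 5.7.1 says patients with symptomatic low blood pressure "should promptly seek medical evaluation at the clinical study site or another hospital setting". Protocol 6.5.5 makes the central laboratory the default and asks that Table 6 tests done at the clinic also go there in parallel. For extra tests prompted by a safety event or an abnormal result, it says "results may be collected and should be included in the clinical database".

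**The concern.** A single-laboratory rule is sound for by-visit means. It fits less well where a patient is counted once for ever crossing a limit, because one value decides the count. Hyperkalaemia and renal dysfunction are named risks in protocol 1.3.2, and laboratory assessments belong to the primary safety objective. Checks made between visits, after a drug change or at another hospital are the ones most likely to be local. If they are ignored, a patient can appear in listing 13.40 or 13.41 and yet be absent from the by-arm table meant to summarise the same finding. A local-only potassium case would also be missing from the potassium plot in 12.4.9.

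**Working it through.** The plan states no figure on this point, so there is none to reproduce. The check compares the rules and then sets the scale.

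**1. Does the central-only rule reach the count tables?** SAP 4.1.1, headed as summary statistics, includes frequencies and percentages for categorical data. On that reading, 12.4.3 and 12.4.4 are covered. No exception is stated.

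**2. Can a qualifying value be local only?** Yes. Protocol 5.8.1 permits it. The parallel sample in protocol 6.5.5 applies to tests done at the clinic. Protocol 5.7.5 asks for central confirmation of ALT/AST above 3×ULN. Protocol 5.7.3 and 5.7.4 ask for repeat tests of eGFR and potassium without naming a laboratory.

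**3. Would the next scheduled sample recover it?** Not necessarily. If a drug is added at Month 3 (Day 85), the check falls near Day 85 + 14 = Day 99. The next scheduled chemistry is Day 113 (±7). Protocol 1.2 reports that in Study 002 most patients with potassium above 5.5 had it at a single time point, and that it mostly normalised without intervention.

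**4. Is a central off-visit value safe?** Not clearly. The scheduled-only sentence in 3.3.3 would drop the Day 99 value even if it were central. SAP 3.5.2 would keep it for worst-value tables. That plainly covers 12.4.4, but 12.4.3 only by inference, since its text does not speak of worst values.

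**5. What does adverse event reporting pick up?** Protocol 5.7.3, 5.7.4 and 6.5.6.1 require an AE of clinical interest, from any laboratory, in two relevant cases. SAP 3.3.1 and 12.1.2 tabulate hyperkalaemia and acute renal failure AEs by arm.
- Potassium above 5.5 that is confirmed or needs intervention. Table 12.4.3 counts any value above 5.5, so an unconfirmed and untreated local value remains outside.
- An eGFR fall of at least 30% that also goes below 60. Table 12.4.3 needs only the 30% fall. A fall from 95 to 65 is (95 − 65)/95 = 31.6%, which qualifies for the table but not for mandatory reporting. This gap exists only for baselines of at least 60/0.70 = 85.7, because from any lower baseline a 30% fall ends below 60.

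**6. Scale.** Inputs are the Study 002 zilebesiran rates in protocol 1.2 (5.6% for potassium above 5.5, 5.3% for an eGFR fall of at least 30%) and 12 patients per arm, so 24 on zilebesiran. It is an assumption that these rates apply here.

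| Threshold | Expected of 24 | Expected per arm of 12 | P(at least one of 24) |
|---|---|---|---|
| Potassium >5.5 | 24 × 0.056 = 1.34 | 0.67 | 1 − 0.944^24 = 0.75 |
| eGFR fall ≥30% | 24 × 0.053 = 1.27 | 0.64 | 1 − 0.947^24 = 0.73 |

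The documents do not give the share of cases seen only locally. The number lost can therefore only be bounded, between none and all of those expected. One omitted patient is 100/12 = 8.3 percentage points of an arm, or 100/24 = 4.2 points of the pooled zilebesiran group.

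**The case against.** A reader might infer that local-only hyperkalaemia and eGFR falls are never counted by arm. The documents do not support that, because of the reporting duty in step 5. A local potassium of 6.2 mmol/L, for example, falls in the protocol's Table 4 category for urgent evaluation and treatment. Once treated or confirmed, it must be reported and should reach the by-arm hyperkalaemia AE table. Protocol 6.5.6.2 also has AEs recorded from clinically relevant laboratory findings generally. In Study 002, hyperkalaemia was reported in 19 zilebesiran patients and potassium above 5.5 was seen in 17, so AE recording there was not the narrower net in total. The documents do not say whether these were the same patients. The primary endpoint is based on AEs and does not depend on which laboratory was used.

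Other safeguards also count. Central testing is the default, clinic-performed tests should go to both laboratories, and serum chemistry is scheduled at Day 8, Day 15 and monthly to Month 6. SAP 6.1 uses summary statistics for continuous items only, so the reach of 3.3.3 to count tables can be disputed. Protocol 5.7.1 concerns where a patient is evaluated, not chemistry results as such. Protocol 6.5.5 does not establish that every routine two-week local result is entered in the database.

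All of this stands, and it reduces the point. It does not remove it. The AE criteria are narrower than the table thresholds, AEs of clinical interest as a category are only listed (13.21), and a renal event enters the by-arm AE table only if its coded term falls in the acute renal failure query. If the reach of 3.3.3 is unclear, that is itself a reason to settle it in the text.

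**Conclusion.** The point holds in a limited form. On the more natural reading of SAP 3.3.3 with 4.1.1, local-only threshold crossings are excluded from 12.4.3 and 12.4.4, and only AE reporting can bring them into a by-arm count. The cases at risk are an unconfirmed, untreated local potassium above 5.5, and a local eGFR fall of at least 30% that stays at or above 60 and is not recorded as an AE. Both should be uncommon because of the parallel central sample. Any specific rate of loss would be guesswork. The reason to act is the arm size: with fewer than one case of each kind expected per arm at the Study 002 rates, a single omission can empty a row. The conflict between 3.3.3 and 3.5.2 over unscheduled values is a separate defect in the text and does not depend on how often local testing occurs.

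**What to change.** In the SAP:
- Keep central-only data for by-visit means, mean plots and the normal-range shifts in 12.4.2.
- For potassium, creatinine and eGFR in 12.4.3 and 12.4.4, state that any post-baseline value in the period counts, including unscheduled ones, and amend 3.3.3 to agree with 3.5.2.
- In the same tables, add a supplementary by-arm count using central results plus any local results held in the database, with eGFR from local creatinine by the protocol 10.1 formula. Show it beside the central-only count and flag local-only cases.

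The cost is a wording change with a revision-history entry (SAP 1.1), one extra column, and unit conversion of whatever local results were captured. Study conduct does not change. Local and central assays may differ slightly, and the side-by-side counts make any effect of that visible.
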